7.1.7 Other endpoints

Technical success - Hercules balloon: successful introduction and withdrawal of balloon dilation catheter, with accurate balloon positioning, expected expansion diameter reached, no balloon rupture or leakage during operation, and no balloon-related vascular injury.

Balloon rupture: refers to the rupture of balloon dilatation catheter during dilation.

7.2 Study Process

1. Case registration: The Internet registration system will be utilized to register all eligible patients who have been treated with Minos Abdominal Aortic Stent-Graft and Delivery System and who have voluntarily consent to participate in the study.
2. Signing the Informed Consent Form
3. Case screening: Cases are selected according to inclusion and exclusion criteria;
4. Case enrollment
5. Collecting the preoperative and intraoperative data
6. Postoperative follow-up: Imaging follow-up to be conducted in accordance with standard of care at participating sites, to include at 30 days, 6 months, 12 months and annually to 5 years after post-procedure. It is expected that all patients will complete this follow up schedule, but participants will not be excluded in the event that follow up is not completed.
7. Data analysis and summary: All relevant data will be collected and analysed from time to time as the study progress.

Flow chart of study:

Project	Visit1	Visit2	Visit3	Visit4	Visit5	Visit6	Visit (7-10)
Time points	Preoperative	Intraoperative	Discharge	30 days after surgery	6 months after surgery	12 months after surgery	2/3/4/5 years after surgery
Window period ³				±7d	±30d	±60d	±90d
Informed consent ¹	X						
Demographics	X						
Inclusion criteria	X						
Baseline / Disease history	X						
Physical examination	X						
Blood test ²	X		X				
CT	X			X ^{4, 5}	X ⁴	X ⁴	X ⁴
Record of operation process		X					
Evaluation of adverse event		X	X	X	X	X	X

Note:

1. The subjects shall complete the signing of the Informed Consent Form before enrollment into the study. This will ideally be prior to the treatment procedure. The absence of laboratory test and imaging examination shall not be considered as a protocol deviation.
2. Blood examination includes standard of care tests in the study site, likely full blood count and standard liver and kidney function tests.
3. CT images collected outside of the follow-up window after surgery will not be considered as a protocol deviation.
4. CT imaging may not be undertaken at all follow up points if it is not the treating institution's standard of care to do so. In such cases, alternative imaging can be recorded i.e. USS.
5. This study is an observational study. If the patient undergoes a postoperative CT review before discharge for clinical purposes or as part of the treating institution's standard of care, this imaging examination will be accepted as the 30 days follow up CT, and a further CT scan at 30 days need not be undertaken.

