7.1.4 Selection of subjects

Inclusion criteria

To be enrolled, patients must meet all the following criteria:

- Diagnosis of infrarenal abdominal aortic aneurysm
- Plan to treat with Minos™ Abdominal Aortic Stent-Graft and Delivery System
- Voluntary participation and completion of Informed Consent Form, with willingness to participate in follow-up to 5 years post-procedure.

Exclusion criteria

- Subjects in whom use of the Minos™ Abdominal Aortic Stent-Graft and Delivery System is contraindicated.

Indications:

- Abdominal Aortic Stent-Graft and Delivery System is indicated for the treatment of abdominal aortic aneurysms with a proximal neck length ≥ 15 mm.
- **Contraindications:**
 - Severe stenosis or calcification near the aneurysm, leading to difficulty in achieving apposition of vessel wall and stent graft.
 - Difficult access due to severe stenosis or tortuosity in the iliac artery or femoral artery
 - Subjects with ruptured aneurysm or acute aneurysm
 - Subjects with an infectious aneurysm.
 - Those who are allergic to contrast agents or unable to tolerate contrast agents due to renal insufficiency.
 - Patients with severe coagulation disorder and/or high risk of postoperative hemorrhage.
 - Aneurysmal neck angulation greater than 60°
 - Patients with blood supply to vital organs originating from the aneurysmal sac.
 - Patients with other comorbidities and whose life expectancy does not exceed one year
 - Subjects with connective tissue diseases, such as Marfan syndrome
 - Minors and pregnant women
 - Subjects who are allergic to nitinol
 - Subjects who are considered not suitable for treatment with stent graft.

Criteria and procedures for termination of the study/treatment

- Should severe safety concerns arise, the study shall be suspended in time.
- If the therapeutic efficacy of the investigational device is found to be poor or ineffective such that it is of no clinical value, the study shall be suspended.
- The discovery of major errors in the clinical trial protocol or significant deviation from it, making it difficult to evaluate the safety and efficacy of the investigational product.
- The sponsor requests suspension (for the reason of funds, management, etc.)
- Revocation is issued by the approving authorities.

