8.1 Population

Full Analysis Set (FAS): set of subjects that are determined according to the "Intention To Treat" principle. Refers to all subjects who signed the Informed Consent Form, met all inclusion and exclusion criteria and were treated with Minos™ system.

Per protocol set (PPS): subset of the full analysis set. Refers to all subjects in whom Minos™ system has been successfully implanted, in whom the main evaluation indicators can be observed, and in whom no significant deviations from the study protocol have been observed.

Safety set (SS): refers to all subjects who have been enrolled and evaluated for safety.

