9.3 Database locking

After completing the data review and confirming the correctness of the established database, the data administrators, principal investigators, sponsor, and monitors shall jointly review the data and complete the final definition and determination of the analysis population. The database will then be locked by the data administrator. The locked database or file may not be modified thereafter.

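### Eligibility may be judged after treatment and decides who is in the full analysis set, so a treated failure could be ruled contraindicated and leave the effectiveness results

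*Protocol*

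**What the plan says.** **Order of events.** Step 1 of Protocol 7.2 uses the online system to "register all eligible patients who have been treated with Minos Abdominal Aortic Stent-Graft and Delivery System", provided they volunteer. Consent is step 2, step 3 reads "Case screening: Cases are selected according to inclusion and exclusion criteria", and enrolment is step 4. The Protocol Summary has the same list. Note 1 to the flow chart requires consent before enrolment; on its timing relative to the operation it says only "This will ideally be prior to the treatment procedure".

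**Signals the other way.** The flow chart puts consent, a row for inclusion criteria and a CT at the preoperative visit, though it has no row for exclusion criteria. One inclusion criterion in 7.1.4 is prospective: "Plan to treat with Minos™ Abdominal Aortic Stent-Graft and Delivery System".

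**Exclusions.** The single exclusion in 7.1.4 is any contraindication to the device, and 13 are listed. One is stenosis or calcification "leading to difficulty in achieving apposition of vessel wall and stent graft". One is difficult access through diseased iliac or femoral arteries. The last is "Subjects who are considered not suitable for treatment with stent graft". None of these three gives a threshold, an assessor or a time point.

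**Analysis sets.** The full analysis set (FAS) in 8.1 invokes the intention-to-treat principle but is limited to consented, treated subjects who "met all inclusion and exclusion criteria". The per-protocol set (PPS) is a subset of the FAS and requires successful implantation. The safety set is enrolled subjects evaluated for safety, with no eligibility condition. Under 8.2, effectiveness is analysed in the FAS and PPS only.

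**Final say.** Under 9.3, data administrators, principal investigators, the sponsor and monitors review the data together and "complete the final definition and determination of the analysis population" before lock.

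**The concern.** In a single-arm registry the denominator carries the result, because no control group would reveal a shift. Membership of the main effectiveness set should therefore be fixed by facts that predate the outcome. Here it depends on eligibility, part of eligibility is open judgement, and nothing requires that judgement to be made and recorded before the operation.

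The three open contraindications also lie close to the endpoints. Under 7.1.6, failed introduction or inaccurate positioning is an immediate technical failure. Under 7.1.5, success during follow-up presupposes technical success and the absence of continuous type I and III endoleaks. A failed delivery through a diseased iliac artery, or a proximal leak at a calcified neck, is thus both an endpoint failure and a case that someone could in good faith call contraindicated in hindsight. If that is done more readily for failures than for successes, the success rates are biased upwards.

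**Working it through.** **Step 1: is screening after treatment allowed?** The 7.2 list, read in order, places it after treatment, and note 1 leaves room for that. But the list cannot be strictly chronological: step 1 already speaks of eligible, consenting patients, and step 5 collects preoperative data after enrolment. With the flow chart and the planned-treatment criterion pointing the other way, the text permits late screening without prescribing it.

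**Step 2: where does a treated patient go if judged contraindicated late?** Applying 8.1 and section 14:

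| When judged contraindicated | FAS | PPS | Safety set | Major deviation reported |
|---|---|---|---|---|
| After treatment, before enrolment | out | out | out | no, never enrolled |
| After enrolment, up to the pre-lock review | out | out | in | yes |

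The PPS already requires successful implantation, so the FAS is the only effectiveness set that could hold an implantation failure.

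**Step 3: does the protocol treat such patients consistently?** No. Section 8.1 drops them from the FAS. Section 14 counts their inclusion as a major deviation. Section 8.6 predesignates a subgroup with neck angle above 60°, which 7.1.4 lists as a contraindication, and describes it as additional to the analysis of the full and per-protocol sets. These passages must be reconciled.

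**Step 4: how large could the effect be?** The protocol gives no figure for this, so what follows is illustration.

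- Inputs: N = 200 (8.3). Success 89%, from the earlier clinical investigation reported in section 4; check: 121/136 = 88.97%, which agrees. Using it as the true rate here is an assumption.
- Successes S = 0.89 × 200 = 178; failures = 200 − 178 = 22.
- If k failures and no successes are removed, the observed rate is S/(N − k). Intervals are exact (Clopper-Pearson) 95%.

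| k (assumed) | Rate | 95% interval | Shift |
|---|---|---|---|
| 0 | 178/200 = 89.0% | 83.8 to 93.0 | none |
| 2 | 178/198 = 89.9% | 84.8 to 93.7 | +0.9 points |
| 5 | 178/195 = 91.3% | 86.4 to 94.8 | +2.3 points |
| 10 | 178/190 = 93.7% | 89.2 to 96.7 | +4.7 points |

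At k = 2 or 5 the estimate stays inside the interval for all 200 patients; at k = 10 it passes that interval's upper limit of 93.0%.

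**The case against.** The strongest reply is that the protocol intends preoperative screening and already has safeguards.

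- *Screening is planned before surgery.* The preoperative column and the planned-treatment criterion support this. It stands to the extent that a reader who infers that exclusions are applied after treatment as a rule goes beyond the text. What remains is a conflict between passages and no rule that freezes the decision.
- *The difficulty items name anatomical causes* that the scheduled preoperative CT can show, and ten of the 13 contraindications are of a different, mostly more objective kind. This is fair: the items need not describe what the operator met during the case. But they still have no threshold, and the third open item names no cause.
- *Failures do not vanish.* A reader might infer that a reclassified case drops out of all results. For an enrolled patient that is wrong: the case stays in the safety set, section 14 has it reported as a major deviation, and deployment failure, access-vessel injury and type I/III endoleak count as device-related adverse events under 13.1. The inference holds only for a patient screened out before enrolment.
- *Pre-lock population review is ordinary, and detailed allocation rules may sit in an analysis plan that is not shown.* Both are true. The difficulty is that the protocol itself conditions the FAS on eligibility, and 9.3 states no masking to outcome for this step.
- *Film reading is blinded and an independent events committee adjudicates (7.1.3).* These protect how outcomes are assessed, not who is counted.
- *The numbers reclassified are invented.* They are assumptions, and the documents do not say what share of failures relates to access or apposition. The table shows scale, not a forecast.

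**Conclusion.** The point holds as a structural weakness. The stated rules allow a treated failure to be judged contraindicated after its outcome is known. That removes it from the effectiveness results if it is enrolled, and from every set if it is not. The conclusion rests on the text of 7.1.4, 7.2, 8.1, 8.2 and 9.3, not on the arithmetic.

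The size is unknown. The illustrative shifts of 0.9, 2.3 and 4.7 points assume a true rate of 89%, 200 treated patients and removal of failures only. If successes were removed in the same proportion, the rate would not move. Nothing in the documents shows that such reclassification is intended or will happen. The change is worth making because the bias route is avoidable and no comparator would expose it.

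**What to change.** 1. **7.2 and Protocol Summary:** reconcile the process list with the flow chart.
2. **Flow chart, Visit 1:** make the row *Inclusion and exclusion criteria*. The investigator judges eligibility from preoperative data and signs and dates the decision before the procedure. For patients who consent later, eligibility is judged only from data that existed before the procedure.
3. **Log:** list every patient treated with the device at each site, with the reason for any non-enrolment.
4. **8.1:** define the FAS as all consented subjects in whom Minos implantation was attempted. A contraindication recognised during or after the procedure is recorded as a deviation and does not remove the subject. Results without such subjects appear only as a sensitivity analysis. Reconcile 8.6 with this definition.
5. **9.3:** limit the pre-lock review to confirming set membership from the preoperative record.

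The cost is amendment wording, one dated eligibility field in the eCRF and the log. The reported success rate may be slightly lower, because some patients found contraindicated late stay in. Requiring consent before every procedure is not needed for this. It would end the post-procedure enrolment that note 1 allows and could reduce consecutive capture, so it is a separate trade-off.

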7.1.2 Method selection and its justification

Minos™ Abdominal Aortic Stent-Graft and Delivery System was granted a Registration Certificate for Medical Device in the People's Republic of China in March 2019, Registration No.: GXZZ 20193130182, and was CE-Marked in September 2019, Certificate No.: M.2019.106.12584. This post-marketing, real-world clinical trial will be conducted on this basis. The study is designed as a prospective, multi-centre, observational registry study. Following review and approval of the study protocol and patient informed consent form by the relevant local ethics committee, the Internet registration system will be used to register all patients treated with Minos™ Abdominal Aortic Stent-Graft and Delivery System who consent to participation in the registry. The investigators at participating study sites will determine the eligibility of patients for enrollment in the study according to the inclusion criteria. The participants and investigators will sign the Informed Consent Form as confirmation of the patient consenting to participation in the study. All participants will be followed up in accordance with the study protocol until 5 years after implantation.

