7.1.3 Measures to avoid and reduce bias

This study will be conducted in multiple centers in and outside of China at the same time. The Internet registration system will be used to register all participants. Clinicians in each study site will select those patients that meet the inclusion criteria to minimize any selection bias created by selection of ineligible patients. Standard operating practices will be adopted to reduce performance bias. Objective index data will be collected as much as possible; design and quality control measures will be strictly investigated, sufficient contact with participants will be maintained as far as possible to maximize the follow-up data obtained and to minimize patients and data lost to follow up during the life of the study. The imaging data obtained from follow-up investigations will be evaluated by blind film reading method as part of the study's data analysis stage. The relevant indicators such as device related adverse events and serious adverse events will be determined by an independent Clinical Event Committee and independent data management and statistical analysis will be utilized to avoid evaluation bias.

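### Consent may be signed after the procedure, yet every analysis set depends on consent or enrolment, so early deaths and failures can go uncounted and early results may favour the device

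*Protocol*

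**What the plan says.** Two sets of statements in the protocol point in different directions.

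**Towards consent before the procedure.** The flow chart (Protocol Summary and section 7.2) marks consent at Visit 1, Preoperative. An inclusion criterion in section 7.1.4 is "Plan to treat with Minos™ Abdominal Aortic Stent-Graft and Delivery System".

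**Towards consent after it.** Note 1 to the flow chart sets one firm rule, "The subjects shall complete the signing of the Informed Consent Form before enrollment into the study", and then adds "This will ideally be prior to the treatment procedure". Step 1 of section 7.2 says the internet system will "register all eligible patients who have been treated with Minos Abdominal Aortic Stent-Graft and Delivery System", and the Summary has a matching step. Section 7.1.2 likewise registers treated patients "who consent to participation in the registry".

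**Analysis sets (section 8.1).** The Full Analysis Set "Refers to all subjects who signed the Informed Consent Form, met all inclusion and exclusion criteria and were treated with Minos™ system". The per-protocol set is a subset of it. The Safety Set "refers to all subjects who have been enrolled and evaluated for safety".

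**Bias control (section 7.1.3).** "Clinicians in each study site will select those patients that meet the inclusion criteria to minimize any selection bias"; the sentence goes on to limit this to bias from choosing ineligible patients.

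**The concern.** Consent gates enrolment, and consent or enrolment gates every denominator. If consent can follow the procedure, part of the outcome may be known, or may already have decided who can sign, before a patient is counted. Immediate technical success is settled when the procedure ends. The 30-day MAE composite in section 7.1.6 includes death and intra-procedural blood loss above 1000 ml. A patient who dies first cannot sign, and one who is doing badly may not be approached. A patient who is well at discharge can still be added.

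Each such loss moves the early results in the same direction, in the device's favour. Section 7.1.1 gives assessing risk and identifying new or emerging risks as purposes of the registry, and few early events are expected, so a small number of losses matters. Because note 1 permits late consent, it would not be recorded as a deviation from that note. The protocol also asks for no count of treated patients who were never enrolled.

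**Working it through.** **1. Can a treated patient be in no analysis set?** Full Analysis Set: no signed form, not a member. Per-protocol set: a subset of the Full Analysis Set, so not a member. Safety Set: enrolment is required and note 1 makes consent a condition of enrolment, so not a member. The answer is yes.

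**2. Does another passage close the gap?** Section 12.3 lets a representative sign for an incapacitated subject before participation; it gives no route for a patient who has died. Blinded image reading and the Clinical Event Committee (section 7.1.3) act on enrolled subjects. Continuous enrolment (Summary, section 3.2) and consecutive registration (Summary, step 1) cover patients who consent.

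**3. Inputs for size.** Section 4 gives pre-market results: 30-day MAE 2/136 = 1.47%; 12-month clinical success 121/136 = 88.97%; 12-month all-cause mortality 10/136 = 7.35%. These agree with the rounded figures printed there. Section 8.3 gives 200 subjects. Expected MAEs are 200 × 2/136 = 2.94, about 3. The exact 95% interval for 3/200 is 0.3% to 4.3%.

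**4. Observed MAE rate under late consent.** Let p be the true rate, f the share consenting after the procedure, and q the probability that an event patient in that share is missed. The protocol gives neither f nor q; both are assumed. If no event-free patient is lost, then

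observed rate = p(1 − fq) / (1 − pfq).

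For p = 0.0147, f = 0.10, q = 0.50: 0.0147 × 0.95 / (1 − 0.000735) = 1.40%.

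| f | q | True 1.47% | True 5% |
|---|---|---|---|
| 10% | 50% | 1.40% | 4.76% |
| 50% | 50% | 1.11% | 3.80% |
| 50% | 90% | 0.81% | 2.81% |
| 100% | 90% | 0.15% | 0.52% |

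The 5% column is there because the exact 95% interval for 2/136 runs from 0.18% to 5.21%.

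**5. Effect across endpoints.** Take 200 enrolled at about the pre-market rates (3 MAEs, 178 successes and 15 deaths at 12 months) and add back k treated patients who died early and never consented. The value of k is assumed. Each is counted as a treatment failure; section 7.1.5 does not name death as one, so this is the less favourable choice.

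| k | 30-day MAE | 12-month success | 12-month mortality |
|---|---|---|---|
| 0 | 3/200 = 1.5% | 178/200 = 89.0% | 15/200 = 7.5% |
| 2 | 5/202 = 2.5% | 178/202 = 88.1% | 17/202 = 8.4% |
| 4 | 7/204 = 3.4% | 178/204 = 87.3% | 19/204 = 9.3% |

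Two missed early deaths move 30-day MAE and 12-month success by about one percentage point each. That is large relative to 1.5% and small relative to 89%.

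**The case against.** The strongest reply is that late consent is a tolerated exception, not the design. The preoperative consent visit, the planned-treatment criterion and the wish to enrol continuously all point to consent beforehand. A site that added only patients who did well would go against the enrolment rule. Sections 7.1.6 and 13.1 also expect failed deployment and conversion to open surgery to be recorded. The order of the steps in section 7.2 is loose and need not be a deliberate rule to enrol retrospectively. This stands as evidence of intent, but none of it overrides note 1 or brings in a patient who never consented.

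A reader might infer that anyone enrolled late is guaranteed free of events up to consent. The documents do not support that. Such a patient is guaranteed alive, but could have had a stroke, a myocardial infarction, major blood loss or a technical failure and still have signed and been counted. Losing non-fatal events requires selective approach or refusal, which is possible but not automatic.

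A reader might also infer that one or two of the three expected MAEs would be lost. Losing one of three requires fq = 1/3, for example half consenting late and two thirds of their event patients missed. Losing two requires fq = 2/3. Nothing in the protocol supports either value, and section 4 does not say whether either pre-market MAE was a death. The shifts from 1.47% in the table all stay above 0.3%, the lower end of the interval for 3/200, except in the extreme last row.

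Finally, the study is descriptive, without a formal hypothesis test (section 8.3), and the endpoints most exposed are secondary and early. This limits the severity.

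**Conclusion.** The protocol contradicts itself on when consent is obtained, and the permissive wording lets treated patients who die or fail early drop out of every denominator. The risk runs in the device's favour for immediate technical success, 30-day MAE and early mortality.

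It is a risk and not an established bias. It needs some sites to consent after the procedure, and patients with early events to be enrolled less often than the rest. Under the assumed shares, a true 30-day MAE rate of 1.47% would be seen as anything from about 1.40% to about 0.81%, and lower only if nearly all event patients are lost. The effect on the 12-month primary endpoint is small, about 89.0% against 88.1% with two missed early deaths. Consent dates will identify who enrolled late, but no analysis can recover patients who were never enrolled. The point should be fixed; the documents do not support treating it as fatal to the registry.

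**What to change.** 1. Change note 1 (Summary and section 7.2) so that the form must be signed before the procedure.
2. Reword step 1 in the Summary and section 7.2, and the matching text in section 7.1.2, to refer to patients planned to be treated with the device. This agrees with the inclusion criterion and the preoperative consent visit. It is feasible because ruptured and acute aneurysms are contraindications, so cases are planned.
3. For subjects already enrolled after treatment, keep them in the main tables and flag them from the dated consent form that section 12.1 requires. Report immediate technical success and 30-day MAE with and without them. In the Kaplan-Meier mortality analyses (section 8.2), let them enter at the consent date. Dropping them outright would delete events that were captured and would recover no missing patient.
4. Report, by site, the number of treated patients not enrolled, with reasons, where obtainable.

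The cost is a few wording changes, one analysis flag and a site count. The downside is that a few treated patients not approached in time will not be enrolled; item 4 keeps their number visible.

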3.2 Project contents

The study is designed as a prospective, multi-centre, post-market, real-world observational registry study. Continuous enrollment is to be conducted for all subjects treated with Minos™ Abdominal Aortic Stent-Graft and Delivery System who meet the inclusion criteria and who voluntarily consent to participate in the study. An enrollment duration period of 24 months is expected for this project and initially, 200 subjects (170 in China and at least 30 in Europe) are to be enrolled. Patient follow up – including CT imaging - will be undertaken in accordance with the usual standard of care at participating sites, and is expected to occur at 30 days, 6 months, 12 months and 2-5 years post-procedure.

1. Primary endpoint

- Technical success rate at 12 months

2. Secondary endpoints

- Incidence of major adverse events at 30 days
- Immediate technical success rate
- Incidence of successful aneurysm treatment at 2-5 years
- All-cause mortality up to 5 years post-procedure
- Aortic aneurysm related mortality up to 5 years post-procedure
- Secondary intervention rates up to 5 years post-procedure
- Aneurysm diameter and variation in aneurysm diameter from 30 days to 5 years post-procedure
- Incidence of type I, III endoleaks from 30 days to 5 years post-procedure
- The incidence rate of stent migration, fracture, stenosis, occlusion and distortion from 30 days to 5 years post-procedure

3. Other endpoints: technical success rate of Hercules balloon and incidence of balloon rupture, where applicable.

In this study, immediate technical success rate, technical success rate at 12 months, secondary intervention rate, aneurysm diameter and variation in aneurysm diameter, and the incidence of type I and III endoleaks are used as efficacy indicators of the Minos™ Abdominal Aortic Stent-Graft and Delivery System. The incidence of 30-day major adverse events, all-cause mortality, aneurysm related mortality, stent migration, stent fracture, stenosis, occlusion and distortion are used as safety indicators of the Minos™ Abdominal Aortic Stent-Graft and Delivery System.

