7.1.5 Primary endpoint

Successful aneurysm treatment: on the basis of technical success and during the follow-up period, the absence of aneurysm rupture, continuous type I and III endoleaks after operation, aneurysm enlargement (aneurysm diameter increased by more than 5mm), secondary intervention due to endoleak, stent occlusion or migration, including open surgery and endovascular surgery. Expected secondary interventions will not be included in the analysis.

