Endoleak: recorded after surgery according to imaging appearances. Adjuvant therapy such as balloon dilatation due to intraoperative endoleak shall not be included in the analysis. Type I endoleaks are leaks at the proximal or distal attachment sites. Type II endoleaks are caused by retrograde flow through collateral vessels into the aneurysm sac. Type III endoleaks are holes, defects, or separations in the stent-graft material. Type IV endoleaks represent porous graft walls. Endoleaks observed in the same subject at different follow-up timepoints without and which have not been treated shall be calculated once.

Stent migration: movement of stent greater than 10 mm.

Stent fracture: fracture of the metal wire of the stent framework.

Stent stenosis and occlusion: stenosis of the internal diameter of the covered section of the stent is a narrowing of $\geq 50\%$ as seen on imaging; stent occlusion refers to 100% stenosis of stent detected on imaging.

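### Ultrasound may replace CT at any postoperative visit, but the protocol does not say when fracture, migration and distortion count as assessed or how CT and ultrasound diameters are compared

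*Protocol*

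**What the plan says.** Note 4 in Protocol 7.2, repeated in the Protocol Summary, reads "CT imaging may not be undertaken at all follow up points if it is not the treating institution's standard of care to do so" and continues "In such cases, alternative imaging can be recorded i.e. USS". It is attached to every postoperative CT cell: 30 days, 6 months, 12 months and years 2 to 5. The preoperative CT does not carry it. Note 1 adds: "The absence of laboratory test and imaging examination shall not be considered as a protocol deviation".

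Section 3.2 lists as a secondary endpoint "The incidence rate of stent migration, fracture, stenosis, occlusion and distortion from 30 days to 5 years post-procedure" and classes these findings as safety indicators. Section 7.1.6 defines two of them without naming a modality or a reference scan: "Stent fracture: fracture of the metal wire of the stent framework" and "Stent migration: movement of stent greater than 10 mm".

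A diameter change of more than 5 mm separates enlargement, reduction and stable in 7.1.6. It is also a failure component of the success definition in 7.1.5: "aneurysm enlargement (aneurysm diameter increased by more than 5mm").

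Section 8.1 defines the Safety Set by enrolment and safety evaluation, with no requirement about imaging. Section 8.2 evaluates safety in that set and plans Kaplan-Meier analysis for mortality, secondary intervention and other safety indicators. Section 8.5 limits imputation to the primary endpoint. The one related safeguard is in 7.1.3: "The imaging data obtained from follow-up investigations will be evaluated by blind film reading method as part of the study's data analysis stage".

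**The concern.** The schedule treats the two modalities as alternatives for a visit, while the endpoints differ in what they need from an image. A broken wire, a graft displaced by more than 10 mm or a distorted frame has to be seen on an image that shows the metal frame. That a routine ultrasound of the sac does not reliably do so is a premise from general imaging knowledge; the protocol is silent on it.

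Under that premise, an ultrasound-only visit carries no information on these three findings, yet nothing in the protocol separates it from a visit at which they were looked for and not found. Section 7.1.1 gives one purpose of the registry as identifying new or emerging risks, and late loss of device integrity is such a risk. A missed failure would read as durability.

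The diameter endpoint has a related problem. Every subject starts from a preoperative CT, and note 5 accepts a pre-discharge CT as the 30-day scan. A site that then follows by ultrasound will subtract a CT diameter from an ultrasound diameter and compare the result with a 5 mm limit.

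**Working it through.** **What the text implies for an ultrasound-only subject**

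1. Note 4: the visit may be imaged by ultrasound.
2. Section 3.2: fracture, migration and distortion are safety indicators.
3. Section 8.1: the subject belongs to the Safety Set whichever modality was used.
4. Section 8.2: a percentage with an exact interval, and Kaplan-Meier for other safety indicators. In Kaplan-Meier, a subject still followed with no recorded event stays at risk.
5. Note 1: absent imaging is no deviation, so deviation reporting would not reveal the gap.

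No sentence codes such a subject as event-free, and none takes the subject out.

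**Size of a possible understatement**

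The protocol gives no ultrasound share and no expected rate for these events, so all inputs here are assumptions. Let p be the true rate, u the share with ultrasound only, and let ultrasound detect none of these failures. If those subjects are kept as event-free, the observed rate is p × (1 − u).

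| u | p = 2% | p = 5% |
|---|---|---|
| 15% | 1.7% | 4.25% |
| 25% | 1.5% | 3.75% |
| 50% | 1.0% | 2.5% |

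This is a bound for a single visit. If a share r of the missed failures persists and is seen on a later CT, the cumulative observed rate is p × (1 − u × (1 − r)). With p = 2%, u = 25% and r = 50% (assumed), 2% × (1 − 0.25 × 0.5) = 1.75%, with the event dated late. If ultrasound-only subjects are left out as not assessable, and modality is unrelated to risk, there is no dilution.

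**Precision after restricting the denominator**

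With no events, the exact two-sided 95% upper limit is 1 − 0.025^(1/n).

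- n = 200: 1.8%
- n = 170: 2.1%
- n = 150: 2.4%
- n = 100: 3.6%

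Reporting 0/200 when only 150 subjects could be assessed would therefore claim an upper limit of 1.8% where the data support 2.4%.

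**The 5 mm rule across modalities**

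Let d be the true change, b the average ultrasound-minus-CT difference and s the SD of the measurement error in the change. The chance of calling enlargement is 1 − Φ((5 − d − b)/s). The values of b and s are assumptions.

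| Comparison | d = +3 mm called enlarged | d = +6 mm missed |
|---|---|---|
| CT–CT, s = 1.5, b = 0 | 9% | 25% |
| CT–ultrasound, s = 2.5, b = 0 | 21% | 34% |
| CT–ultrasound, s = 2.5, b = −2 | 5.5% | 66% |
| CT–ultrasound, s = 2.5, b = +2 | 50% | 12% |

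For an unchanged sac (d = 0, b = 0), the false-enlargement chance is 0.6% at s = 2 (5/2 = 2.5), 4.8% at s = 3 and 10.6% at s = 4.

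Over a population with true changes distributed N(−3, SD 5), the true share above 5 mm is P(Z > 8/5) = 5.5%. The observed share is P(Z > (8 − b)/√(25 + s²)). With s = 2.5 this is 7.6% at b = 0, 3.7% at b = −2 and about 14% at b = +2. The direction depends on b, which is unknown.

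**The case against.** Imaging by local standard of care is the deliberate design of an observational registry, and note 4 is conditional on it. Nothing shows how many sites use ultrasound, or that practice differs between China and Europe. This stands, and the point does not ask for more CT.

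A reader might infer that the protocol counts ultrasound-only subjects as event-free and that device-failure rates are therefore understated. The documents do not support that. Section 8.2 does not fix denominators, 8.5 does not fill in a missing fracture as absent, and the blinded readers in 7.1.3 might code such images as not assessable. The understatement is a possible result of following the text, not an established one.

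It may also be said that denominators and modality fields belong in the analysis plan or eCRF, which are not shown and may already deal with part of this. That is fair for the detail. It does not dispose of the point, because the substitution rule, the endpoint definitions and a Safety Set without an imaging condition are all protocol text, and together they lead to a risk set that includes unassessed subjects. Blinded reading cannot recover what an image does not contain.

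Finally, the effect on the 7.1.5 success definition is limited. Migration enters only through secondary intervention, and fracture and distortion during follow-up are not listed. Of the issues raised here, only the diameter rule reaches it directly.

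**Conclusion.** The protocol allows CT and ultrasound to be mixed without stating which visits count as assessed for fracture, migration and distortion, or how diameters from different modalities are compared. The three rates may be understated by an unknown amount, bounded at a single visit by the ultrasound-only share and smaller where a later CT shows the failure. Enlargement and reduction may be misclassified in either direction.

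This rests on three assumptions: that some sites use ultrasound in place of CT, that routine ultrasound does not show these frame failures, and that no document outside the protocol already excludes such visits. The percentages above illustrate scale; they do not estimate bias in this registry. Nothing here shows that stenosis, occlusion or endoleak would be missed. The matter should be settled in the protocol text, because modality that is not recorded prospectively may be hard to recover later.

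**What to change.** Keep standard-of-care imaging and add no scans. Change what counts:

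1. Record imaging modality in the eCRF at every visit.
2. For fracture, migration and distortion, count a visit as assessed only if it has CT or another modality that shows the metal frame. In Kaplan-Meier analyses of these endpoints, censor at the last such visit.
3. Base diameter change on same-modality pairs where they exist, for example with the first postoperative ultrasound as reference at an ultrasound site. Keep cross-modality comparisons but flag them, and report a sensitivity analysis without them. A strict same-modality rule would go too far: the preoperative image is CT, so every comparison with baseline at an ultrasound site would become unclassifiable, gross growth included.
4. Report the CT/ultrasound split beside each rate.

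The cost is one eCRF field and some endpoint wording, plus smaller denominators and wider intervals. With no events, the upper limit rises from 1.8% to 2.4% if 150 rather than 200 subjects are assessable. If modality is related to risk, the restricted rate describes only the subjects with adequate imaging, and the reported split lets readers judge that.
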